5.3.2. Titration Schedule and Dose Adjustments

Subjects randomized to the topiramate arm will start 25mg topiramate once daily in the evening. On day 4 following randomization a morning dose of 25 mg will be added. On day 8 following randomization an additional 25 mg tablet will be added in the evening, and on day 12 a second morning dose will be added so that the subject will be taking a total of 50mg twice daily. Subjects who experience an adverse event during the dose titration may continue at the highest tolerated dose for one week prior to an additional attempt to increase to the targeted dose. Those who are tolerant of a lower dose but intolerant of the target dose will continue on the highest tolerated dose. Results will be analyzed in an intent to treat fashion. If a subject develops a treatment related adverse event, the dose may be lowered at the discretion of the site PI in order to establish a lower maximally tolerated dose. Those who have an adverse event and are unable to continue medication will undergo a termination visit.

In accordance with local regulatory requirements, the investigator, designated site staff, or head of the medical institution (where applicable) must document the amount of investigational product dispensed and/or administered to study subjects, the amount received from the central pharmacy, and the amount destroyed upon completion of the study. An investigator is responsible for ensuring product accountability records are maintained throughout the course of the study. The inventory will include details of *topiramate* received and dispensed to subjects, batch, and ID numbers. All unused *capsules* must be kept until reconciliation of delivery records with accountability logs by the monitor. After the monitor has performed accountability, the site will be instructed by the DCC or designee to either destroy the remaining study drug or return it to the

Central Pharmacy or manufacturer. An accounting must be made of any drug deliberately or accidentally destroyed. Discrepancies between the amount of topiramate received and dispensed drug must be reconciled.

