- Instruct subject about correct administration and titration of study drug. See section 5.3.2.
- Instruct subject to bring unused study drug to each study visit, and to immediately report any AEs to the Investigator or Coordinator.
- Administer the *Neuropathy Total Symptom Score-6* (NTSS-6) to the subject. See section 7.1.9.
- Administer the *Brief Pain Inventory – Diabetic Neuropathy* (BPI-DN) BPI-DN. See section 7.1.9.
- Perform clinical assessment for suicide ideation with the *Columbia-Suicide Severity Rating Scale* (C-SSRS). See section 7.1.15.
- Complete the Rapid Assessment of Physical Activity (RAPA) Survey. See section 7.1.17.

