6.5. Visit 03 Week 16 (± 7 days)

This safety follow-up visit will occur within ± 7 days of the targeted visit date. The following procedures will be performed at the Week 16 visit (this visit may take about 3 hours):

- Review interval medical history.
- Review adverse events.
- Review concomitant medications, including all nutritional, herbal and alternative therapies. See section 7.1.4.
- Perform vital sign measurements: blood pressure (systolic and diastolic), heart rate (beats/minute), and body temperature (°C). See section 7.1.6.
- Record weight (kg) and Body Mass Index (BMI).
- Record waist circumference (cm). See section 7.1.7.
- Perform an Abbreviated Physical Examination including visual field examination and assessment for fall risk.

- Administer the *Utah Early Neuropathy Scale* (UENS). See section 7.1.10.
- Collect blood samples for safety monitoring laboratory assessments including basic metabolic panel, CBC and serum pregnancy test (pregnancy test for women of child-bearing potential only). (Refer to University of Rochester Medical Center Lab Manual for sample handling and processing requirements). See section 7.1.12.
- Dispense study drug.
- Perform study drug reconciliation and container collection.
- Assess study drug compliance.
- Administer the *Neuropathy Total Symptom Score-6* (NTSS-6) to the subject. See section 7.1.9.
- Administer the *Brief Pain Inventory – Diabetic Neuropathy* (BPI-DN) BPI-DN. See section 7.1.9.
- Administer the *Norfolk Quality of Life-Diabetic Neuropathy scale* (NQOL-DN). See section 7.1.19.
- Perform clinical assessment for suicide ideation with the *Columbia-Suicide Severity Rating Scale* (C-SSRS). See section 7.1.15.

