6.13. Early Termination and Premature Withdrawal

Subjects have the right to withdraw from the study at any time without prejudice. The site Investigator may withdraw study drug from a subject in the study in the event of intercurrent illness, adverse events, other reasons concerning the health or well-being of the subject or other administrative reasons. Early termination will be implemented in the case of emergency disclosure of drug treatment (i.e., unblinding). **NOTE: All efforts should be made by study staff to encourage subjects to return for follow-up visit(s). If a subject withdraws consent from the study in writing, no further contact can be made.**

A subject may discontinue study medication for the following reasons:

Administrative

1. Withdrawal of consent
2. Request of Sponsor or Principal Investigator
3. Request of primary care physician
4. Pregnancy
5. Subject deemed lost to follow up/failure to return
6. Termination of study
7. Other

Adverse Event

1. Worsening of the disease under study
2. Worsening of pre-existing disease (other than disease under study)
3. Intercurrent illness
4. Death
5. Major/clinically significant alteration in laboratory values after beginning study drug
6. Suicidality based on the C-SSRS
7. Other adverse event

In the event a participant discontinues study medication for any reason, every effort should be made to complete the evaluation visits at week 32, 64, and 96. An early termination visit should be completed for all participants who are unable or unwilling to complete additional evaluation visits. If a subject is unable to return to the site, or refuses to complete all termination visit procedures, any reasonable study procedures to which the subject consents will be completed.

Should a scheduled in-person visit be impossible, conduct as many of the verbal assessments as possible, with special emphasis on obtaining information on possible AEs, and arrange for return of study drug. Every effort will be made to determine the subject's health status at withdrawal.

Reasons for early termination of the subject prior to completion of the study must be stated in the CRF and in the site source documentation for all study subjects who were enrolled in the study. The CCC and the IMM must be informed within 24 hours of all study subjects who are withdrawn due to an adverse event.

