6.13.2. Restarting Study Drug after Premature Drug Discontinuation

Subjects who discontinue study drug for less than one week will be asked to restart at the prior dose. Those who failed to take study drug for 1-7 days will be asked to restart at the previous dose. Those not having taken study drug for 8-14 days will restart at half of the prior dose. Those not having taken study drug for 15 days or more will restart the titration. Those who discontinued due to an adverse event will restart at a dose lower than the maximally tolerated dose and titrate to that dose.

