8. MANAGEMENT OF ADVERSE EVENTS

Extensive data regarding safety and adverse events are available from clinical trials of topiramate for epilepsy and episodic migraine. The dose of topiramate to be used in the TopCSPN Study is similar to that used for episodic migraine (50-200mg daily). Adverse events observed in randomized trials for migraine will be summarized⁶⁵. Following this summary, potentially significant adverse events observed at higher doses will be listed.

When topiramate must be discontinued for participant safety, the dose can be stopped immediately or titrated down based on the clinical judgement of the site investigator.

Adverse Events Observed at 100 mg daily of topiramate:

- Anorexia. Loss of appetite is one of the mechanisms contributing to weight loss. Most commonly anorexia is mild. In subjects complaining of intolerable anorexia, the dose will be tapered to the maximal tolerated dose.
- Fatigue. Subjects complaining of intolerable fatigue will be asked to taper the dose to the maximum tolerated.
- Memory Problems. Topiramate may cause confusion, psychomotor slowing, poor concentration, or memory loss. These symptoms are more commonly observed with rapid dose escalation. Patients complaining of intolerable memory problems, or those observed to have cognitive dysfunction sufficiently significant to warrant dose modification in the opinion of the PI will taper their dose to that maximally tolerated.
- Nausea. Subjects complaining of intolerable nausea will be asked to taper the dose to the maximum tolerated.
- Paresthesias. Paresthesias are typically mild and uncommonly lead to discontinuation. In the setting of this study, paresthesias may also be related to the underlying disease (CSPN), or nerve regeneration. There are no data suggesting topiramate causes or worsens peripheral neuropathy. Subjects experiencing increased paresthesias will be encouraged to continue to participate unless the symptom is severe enough in the opinion of the PI to warrant dose reduction.

Potentially serious adverse events noted in the package insert include:

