- Glaucoma. Topiramate has been reported to cause acute myopia associated with secondary angle closure glaucoma. Symptoms typically occur within 1 month of initiating therapy, and include decreased visual acuity and ocular pain. Ophthalmologic findings can include myopia and ocular hyperemia (redness). Mydriasis may or may not be present. Visual acuity will be assessed at each visit and subjects with reduced acuity, ocular pain, or ocular hyperemia will discontinue medication and be immediately referred for ophthalmologic examination.
- Kidney stones. 1.5% of adults exposed to topiramate during its adjunctive epilepsy therapy development reported the occurrence of kidney stones, an incidence about 2 to 4 times greater than expected in a similar, untreated population. Carbonic anhydrase inhibitors (Topiramate, but also zonisamide, acetazolamide or dichlorphenamide) can promote stone formation by reducing urinary citrate excretion and by increasing urinary pH.
- Metabolic acidosis. Hyperchloremic, non-anion gap, metabolic acidosis (i.e., decreased serum bicarbonate below the normal reference range in the absence of chronic respiratory alkalosis) is caused by renal bicarbonate loss due to the inhibitory effect of topiramate on carbonic anhydrase. Renal disease, severe respiratory disorders, status epilepticus, diarrhea, and ketogenic diet may increase this risk. Symptoms may include hyperventilation, fatigue, anorexia, or rarely cardiac arrhythmias or stupor. Serum electrolytes including bicarbonate will be measured at each study visit. Subjects with a total bicarbonate of < 17 mEq/L and a > 5 mEq/L decrease from pretreatment will discontinue treatment.
- Oligohidrosis (decreased sweating) and subsequent loss of temperature regulation with hyperthermia has been reported in adults, especially in combination with carbonic anhydrase inhibitors and anticholinergic medications. Subjects complaining of significant reduction in sweating will taper medication to the maximum tolerated dose.
- Visual field defects (independent of elevated intraocular pressure) have been reported in clinical trials and in postmarketing experience. Visual fields will be assessed at each study

visit. Patients observed to have new visual field abnormalities will be referred for ophthalmologic examination and medication will be discontinued.

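### Section 8 expects topiramate-related acute myopia with angle closure within about a month of starting, but its first post-dose acuity check is at week 16 and no earlier contact described names an eye symptom

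*Combined protocol and SAP*

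**What the plan says.** The glaucoma item in Section 8 gives both the timing and the response. On timing: "Symptoms typically occur within 1 month of initiating therapy, and include decreased visual acuity and ocular pain". On response: "Visual acuity will be assessed at each visit and subjects with reduced acuity, ocular pain, or ocular hyperemia will discontinue medication", followed by immediate referral to ophthalmology. The section opens its account of the more serious events with "Following this summary, potentially significant adverse events observed at higher doses will be listed", although the list itself is headed as coming from the package insert.

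Section 5.3.2 brings participants to full dose quickly: "on day 12 a second morning dose will be added so that the subject will be taking a total of 50mg twice daily". The first clinic visit after dosing is week 16, for which Section 6.5 says "This safety follow-up visit will occur within ± 7 days of the targeted visit date".

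Before that visit the plan describes these contacts and safeguards:

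- Section 6.4, at dispensing: "Instruct subject to bring unused study drug to each study visit, and to immediately report any AEs to the Investigator or Coordinator".
- Section 7.1.18 and Appendix A footnote 2: monthly calls, at weeks 4, 8 and 12 in this interval, made for compliance and retention.
- Section 11.4.2: one open question about problems or symptoms, asked at visits and telephone interviews.
- Section 6.11: unscheduled safety visits are possible.
- Section 4.2, criterion 23: closed angle glaucoma can exclude a candidate, in the site investigator's opinion.

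**The concern.** The plan names a harm, says when it usually appears, and ties the scheduled check to visits that begin well after that period. The stop-and-refer rule can act only once someone recognises a symptom. In the first month, in the text available, recognition depends on the participant treating an eye symptom as reportable, or mentioning it in reply to a general question at the end of the month. What is at stake is the safety of participants on topiramate: how soon drug is stopped and an eye examination arranged.

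A smaller point concerns the hand-off. Footnote 2 has coordinators making the calls, while Section 11.4.2 leaves action on study drug to the investigator. No time is set for passing on a call answer. The limits in Section 11.4.2 (24 hours for serious events, 5 working days for others) govern reporting to the coordinating center.

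**Working it through.** The plan gives no figure of its own to reproduce. The check sets its calendar against its onset statement.

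**Inputs.** Onset typically within 1 month (Section 8), taken as day 30. Baseline and dispensing on day 0 (6.4). Full dose from day 12 (5.3.2). First post-dose visit at week 16 ± 7 days (6.5). First call at week 4 (7.1.18). 125 participants in two arms (Section 3). 14 + 1 = 15 sites (4.4).

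**Dates.**

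- Week 16 = 16 × 7 = day 112; with the window, 112 − 7 = day 105 to 112 + 7 = day 119.
- Distance from the end of the onset period: 105 − 30 = 75 days to 119 − 30 = 89 days. Taking a month as 28 or 31 days shifts both by at most 2 days.
- Week 4 call = 4 × 7 = day 28, which is 28 − 12 = 16 days after full dose starts and 30 − 28 = 2 days before day 30.

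**Contacts in the first 30 days.** Post-baseline visits: 0 of 6 (weeks 16, 32, 48, 64, 80, 96). Scheduled calls: 1.

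**What each route names.**

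| Route | When | Names reduced vision, eye pain or redness? |
|---|---|---|
| Dispensing instruction (6.4) | From day 0 | No; any adverse event |
| Week 4 call (7.1.18, footnote 2) with open question (11.4.2) | Day 28 | No; any problem or symptom |
| Unscheduled safety visit (6.11) | Any time | No; needs a prior report |
| Acuity check (Section 8) | Day 105 to 119 | Yes, through the Section 8 rule |

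That the open question reaches the monthly calls is the natural reading of 11.4.2. On a narrower reading of what counts as a telephone interview, the week 4 call would carry no symptom question.

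**Exposure.** 125 / 2 = 62.5, so about 62 or 63 participants on topiramate.

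**Call time for a direct question (minutes assumed).** 125 × 1, 2 or 3 min = 2.1, 4.2 or 6.3 hours for the trial. Per site, 125 / 15 = 8.3 participants, so about 8 to 25 minutes.

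**Benign complaints at that call (rates assumed).** At 1%, 5% or 10%, 125 × rate = 1.25, 6.25 or 12.5 participants. These are illustrations, not an upper limit: the documents give no rate, and a dispensing instruction invites reports over all 96 weeks.

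**The case against.** The strongest reply is that the month is already covered. Participants must report any adverse event at once, Section 11.4.1.1 defines an adverse event widely enough to include eye pain, redness or loss of vision, and the open question gives a scheduled symptom check at week 4. The stop rule for pain and redness is not confined to visits. The consent form, which Section 12.1 says describes risks, would be a natural place for a warning, and its pages were removed from the public file. All of this stands, and it makes the gain modest. A consent warning would strengthen the dispensing instruction, but would not supply a recorded week 4 question or a same-day hand-off.

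It is also fair that week 4 falls near the end of the expected period, so the direct question alone adds little early recognition. The dispensing instruction does most of the early work.

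The reference to higher doses weakens the point only a little. Section 8 ties onset to starting therapy, gives no dose threshold, and applies the stop rule to this trial's participants.

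A reader might infer three stronger things that the documents do not support:

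- That there is no eye-safety monitoring in month 1. The routes above contradict this.
- That detection would be delayed by 75 to 89 days. Self-report and the week 4 call come earlier.
- That the timing applies to all ocular toxicity. The one-month statement covers acute myopia with angle closure; the separate item on visual field defects gives no onset time.

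**Conclusion.** The point holds in a limited form. Followed exactly, the plan places its first scheduled post-dose check for this harm after the period in which it says symptoms typically appear, and none of the earlier contacts described names the symptoms that trigger its own rule. The week 16 check keeps its value for later cases.

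The improvement is cheap and of modest size, and worth making. No number of cases prevented or detected earlier can be claimed, since the documents give no incidence at 100 mg daily. The conclusion rests on a month of about 30 days, on the natural reading that the open question applies to the calls, and on the visible text only. If the consent form already lists these symptoms with an instruction to call at once, the gain shrinks further.

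**What to change.** 1. Extend the dispensing instruction in Section 6.4: new reduced vision, eye pain or eye redness is to be reported the same day.
2. In Section 7.1.18 and Appendix A footnote 2, add a direct, recorded question on these three symptoms to the existing week 4 call, in both arms so that the blind is kept.
3. Pass any positive answer to the site investigator the same day, and apply the Section 8 stop-and-immediately-refer rule as written. No confirmation step should come before it, because that would put discretion in front of a rule that is now unconditional.

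No visits or calls are added. The cost is the call time worked out above, a small data field, and an amendment, which under Section 9 needs written approval from the sponsor and the central IRB.

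The main downside is an unknown number of extra referrals and drug stops for benign complaints, since Section 8 sets no severity threshold. Some stops could become early terminations: Section 5.3.2 sends those unable to continue medication after an adverse event to a termination visit. Two provisions soften this. For participants off drug, Section 6.13 says "every effort should be made to complete the evaluation visits at week 32, 64, and 96". Section 6.13.2 gives a restart path that could be used if the eye examination is normal: "Those who discontinued due to an adverse event will restart at a dose lower than the maximally tolerated dose".

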8.1. Pregnancy

Pregnancy itself is not regarded as an AE unless there is a suspicion that the study drug may have interfered with the effectiveness of a contraceptive medication. However, the outcome of all pregnancies that occur during paternal or maternal exposure to study drug (spontaneous miscarriage, elective termination, normal birth or congenital abnormality) must be followed up and documented even after the subject has been withdrawn from the study. All reports of congenital abnormalities/birth defects are SAEs. Spontaneous miscarriages should also be reported and handled as SAEs. Elective abortions without complications should not be handled as AEs. All outcomes of pregnancy must be reported to the Coordination Center.

9. PROTOCOL AMENDMENTS AND STUDY TERMINATION

All revisions and/or amendments to this protocol must be approved in writing by the Sponsor and the CIRB. The Investigator will not make any changes to the conduct of the study or the protocol without first obtaining written approval from the Sponsor and the CIRB, except where necessary to eliminate an apparent immediate hazard to a study subject.

The Sponsor and NeuroNEXT Network reserve the right to discontinue the study at a clinical study site(s) for safety or administrative reasons at any time. Should the study be terminated and/or the clinical study site closed for any reason, all documentation and study drug pertaining to the study must be returned to the Sponsor or its representative.

10. STATISTICAL CONSIDERATIONS

The NeuroNEXT Data Coordinating Center has developed a statistical analysis plan, in collaboration with the protocol principal investigator and protocol steering committee.

a. General considerations. Univariate summaries will be provided for all randomized subjects and by treatment group. Transformations will be considered for continuous variables exhibiting substantial skewness. Analyses of topiramate's effect will be conducted according to randomized treatment assignment in accordance with the intent-to-treat principle.

b. Strategy for evaluating the Co-Primary Endpoints in Aim 1. Analyses of the effects of topiramate on the co-primary endpoints will be interpreted from two perspectives. From a scientific investigational perspective, IENFD and NQOL-DN will be viewed as representing separate outcome domains, and the hypotheses of treatment effects on these outcomes will be considered conceptually distinct. Because positive findings from this early-phase trial will be subjected to confirmation in a subsequent pivotal trial, the scientific hypotheses of treatment effects on the conceptually distinct co-primary endpoints will be tested on a comparison-wise basis without multiple comparison adjustment in order to enhance statistical power^{74,75}. From a decision-

theoretic perspective, the results of this early-phase clinical trial will be applied to determine whether to proceed to a larger pivotal trial with a definitive clinical endpoint. Proceeding to a full-scale trial will be deemed appropriate if the present trial demonstrates that topiramate has a benefit based on either IENFD or NQOL-DN and does not have an adverse effect the other outcome. Because this choice represents a single decision point, a single global decision rule to control the risk of inappropriately proceeding to a full-scale trial will be applied. The analyses of the effect of topiramate on the IENFD and NQOL-DN as distinct endpoints are described first, followed by a global strategy for deciding whether to proceed to a full-scale trial.

c. Analysis of Co-Primary Endpoints. We hypothesize that topiramate will reduce the rate of deterioration of IENFD over the full follow-up period. Hence the primary analysis of the IENFD will compare the mean IENFD slope between the treatment and control groups under a longitudinal model with fixed effects for baseline IENFD, age, baseline BMI randomization stratification group, follow-up time (as a continuous variable), and the interaction between treatment assignment and follow-up time. Inclusion of baseline IENFD as a covariate will increase statistical power in a similar fashion as adjustment for the baseline level of the outcome in a conventional analysis of covariance. Expressed mathematically, the longitudinal model for IENFD is: $Y_{it} = \alpha_0 + Y_{i0} \beta_0 + \text{Age} \beta_1 + [\text{BMI Group}] \beta_2 + Y_{i0} \times \text{time}_{ij} \times \beta_3 + T_i \beta_4 + \text{time}_{it} \beta_5 + T_i \times \text{time}_{it} \beta_6 + \varepsilon_{it}$, $\text{Var}(\varepsilon) = \Sigma$, $i = 1, 2, \dots, N$, $t = 0, 1, 2, 3$, where Y_{it} denotes the IENFD measurement for patient i at visit t , with $t = 0$ representing the baseline visit so that Y_{i0} is the baseline IENFD, T_i denotes the randomized treatment group for the i th patient (with $T_i = 1$ for the topiramate group, and $T_i = 0$ for the control group), time_{it} denotes the time of the t^{th} IENFD measurement for patient i , $T_i \times \text{time}_{it}$ denotes the treatment by time interaction, and the ε_{it} denote residuals of the IENFD measurements which are assumed to be normally distributed with a covariance matrix Σ which is described below. The coefficient β_6 represents the effect of the topiramate treatment on the mean IENFD slope over time. We will use a general unstructured covariance model for Σ ⁷⁶ so that the full model represents a special case of the linear mixed model^{76,77} that allows for all possible correlations among the residuals among the IENFD measurements. When the number of time points is small relative to the number of subjects as is the case for IENFD in this proposal, the general unstructured covariance model is widely used in randomized trials because it provides essentially identical statistical power to that obtained under less general covariance models while avoiding the need for post-hoc modifications to satisfy modeling assumptions⁷⁶. Estimates of the model coefficients and standard errors will be obtained by restricted maximum likelihood estimation (RMLE)⁷⁸.

Topiramate may have direct effects on QOL that are independent of CSPN progression and which may occur shortly after treatment initiation, as well as longer term effects that result from effects of topiramate on neuropathy progression. Accordingly, the primary analysis of the NQOL-DN will compare the total mean change in the NQOL-DN from baseline to 2 years between the treatment and control groups under a longitudinal model that includes linear spline terms to allow separate mean slopes during the first 12 weeks after randomization and from 12 weeks to the end of follow-up. Age, baseline BMI group and baseline NQOL-DN will be treated as a covariates to increase statistical power. In addition to the primary comparison of the total mean change in

the NQOL-DN to 2 years, linear contrasts will be constructed to estimate the effect of the treatment on the early change in the NQOL-DN to 16 weeks, and on the longer-term NQOL-DN slope after 16 weeks. Expressed mathematically, the mixed effects model for the NQOL-DN is: $Y_{it} = \alpha_0 + Y_{i0} \beta_0 + \text{Age} \beta_1 + [\text{BMI Group}] \beta_2 + Y_{i0} \text{timlo}_{it} \beta_3 + Y_{i0} \text{timhi}_{it} \beta_4 + T_i \beta_5 + \text{timlo}_{it} \beta_6 + \text{timhi}_{it} \beta_7 + T_i \times \text{timlo}_{it} \beta_8 + T_i \times \text{timhi}_{it} \beta_9 + \varepsilon_{it}$, $\text{Var}(\varepsilon_{it}) = \Sigma$, $i = 1, 2, \dots, N$, $t = 0, 1, 2, \dots, 6$, where Y_{it} denotes the NQOL-DN measurement of the i^{th} patient at visit t , $\text{timlo}_{it} = \min(0, \text{time}_{it} - 16 \text{ weeks})$ and $\text{timhi}_{it} = \max(0, \text{time}_{it} - 16 \text{ weeks})$ represent linear spline terms in follow-up time, and the remaining terms are analogous to those defined in the model for the IENFD described above. Accounting for separate slopes in the first 16 weeks and the subsequent 80 weeks, the primary linear contrast defining the treatment effect on the mean change to 2 years is $4 \times \beta_8 + 20 \times \beta_9$. Due to the relatively large number (6) of follow-up measurement times for the NQOL-DN, an unstructured covariance model may lead to inefficient estimation⁷⁶, and a relatively parsimonious covariance model will be used to limit the number of unknown parameters to be estimated⁷⁶. Standard covariance models to be considered include models with random intercepts and slopes combined with an autoregressive or Toeplitz covariance matrix for the residuals around the underlying trajectories⁷⁹⁻⁸¹. The covariance model will be selected from a pre-specified collection of potential models by comparing BIC statistics under maximum likelihood estimation⁸¹. After selection of the covariance model, final statistical inferences will be performed using restricted maximum likelihood estimation as in the analyses of the IENFD outcome.

d. Missing Data. Because statistical inference is based on restricted maximal likelihood (REML) estimation, the longitudinal analyses described above will remain unbiased in the presence of missing data which follows a missing at random mechanism⁸²; sensitivity analyses will be conducted using multiple imputation of missing data⁸³ under imputation models which incorporate auxiliary variables to account for predictors of missingness and/or the variables being analyzed beyond those in the analytic model.

e. Statistical Power for Separate Analyses of the Co-Primary Endpoints. Statistical power for IENFD was estimated by first fitting a mixed effects model to the first 2 years of follow-up for 116 subjects from the Utah Diabetic Neuropathy Study natural history cohort with baseline MNSI ≥ 3 , indicating the presence of neuropathy symptoms. This cohort, as described in the preliminary data, excluded patients with longstanding neuropathy and is thus appropriate given the phenotypic similarity with CSPN. This analysis yielded variance components for IENFD trajectories over time and within-subject residuals. A design matrix was then constructed for the planned measurement schedule for the topiramate trial with IENFD measurements at baseline and weeks 32, 64 and 96 but with 4% loss-to-follow-up every 32 weeks for a total 12% loss-to-follow-up over 96 weeks. Using this design matrix and the variance components estimated from the preliminary data, 125 randomized subjects will provide 80% power with 2-sided $\alpha=0.05$ to detect a difference in mean IENFD slope between the treatment and control groups of 0.47 fibers/mm/year. An effect of 0.47 fibers/mm/year represents a reduction in the mean slope from -0.68 fibers/mm/year observed in our preliminary data to -0.21 fibers/mm/year. This projected effect size is conservative given preliminary data that successful intervention may result in

improvement in IENFD rather than just slowing of its rate of decline^{10,12,13}. Statistical power for the NQOL-DN was estimated based on an assumed SD for change in the NQOL-DN score over 2 years of 16.4 points, which conservatively allows for a 10% higher SD than the SD of 14.9 points reported for the change in the NQOL-DN in Boyd *et al*²⁴. If the correlation between baseline and follow-up assessments is ≤ 0.60 , 125 subjects with 12% loss to follow-up will provide 80% power with 2-sided $\alpha=0.05$ to detect a mean difference of 7.9 points between the treatment and control groups over 96 weeks after adjustment for the baseline NQOL-DN. This represents a difference of 4.0 points per year. This power calculation is conservative, as the multiple repeated QOL measurements in the study design will provide greater precision than the simplified ANCOVA based on a single follow-up time considered in this power calculation.

f. Decision for proceeding to a full-scale trial (“Go/No-Go” Algorithm). A full-scale trial will be justified if topiramate is demonstrated to be superior to placebo for either IENFD or NQOL-DN, and non-inferior for both of these outcomes. We estimated non-inferiority margins of up to 0.50 fibers/mm/year for the IENFD slope and up to an average of 5 points per year for the NQOL-DN. A failure to proceed to the full-scale trial would be problematic if there is a treatment benefit of 0.50 fibers/mm/year for the IENFD or of an average of 5.0 points per year for the NQOL-DN and the treatment does not have an adverse effect on the other outcome. Based on these conditions, the following global decision rule was developed: Proceed to the full scale trial if either:

1. The comparison of randomized groups favors topiramate by at least 0.30 fibers/mm/yr for IENFD and favors the placebo by no more than 2.70 points per year for the NQOL-DN, or
2. The comparison of randomized groups favors topiramate by at least 2.97 points per year for the NQOL-DN & favors the placebo by no more than 0.22 fibers/mm/yr for the IENFD.

Given the previously stated assumptions for the analyses of IENFD and NQOL-DN as separate endpoints, and assuming a Pearson R of -0.30 between the IENFD and QOL-DN based on Boyd *et al*²⁴, numerical integration of the bivariate normal distribution implies that this global decision rule has a Type 1 error $\leq 5\%$ for an inappropriate recommendation to proceed to a full scale trial given inferiority for at least on outcome or absence of superiority for both outcomes, and Type 2 error $\leq 18\%$ for failure to recommend proceeding to the full scale trial when the stated criteria for superiority of at least 1 outcome and non-inferiority for both outcomes are satisfied.

g. Secondary outcomes. Treatment effects on continuous secondary outcomes which are either approximately normally distributed or can be transformed to approximate normality will be analyzed using linear mixed effect models similar to those described for IENFD and NQOL-DN. Generalized linear mixed models with outcome models appropriate to each outcome variable will be applied for ordered categorical outcomes measured at the scheduled follow-up visits and for continuous outcomes that cannot be transformed to achieve approximate normality. The treatment effect on the rate of falls will be estimated using negative binomial regression.

g. Evaluation of the clinical meaning of IENFD change. A major secondary objective of the TopCSPN study is to explore the clinical meaning of change in IENFD. TOPIRAMATE may

potentially affect NQOL-DN and other clinical endpoints (e.g., balance, fall risk) through *direct effects* that are independent of neuropathy progression (IENFD), or through *indirect effects*, which are mediated through a pathway that incorporates effects of the treatment on neuropathy progression based on IENFD. Using this conceptual framework, mechanistic information will be obtained from three types of analyses:

M1) Evaluation of the profile of treatment effects on the QOL-DN and other clinical endpoints in comparison to the treatment effect on the IENFD,

M2) Evaluation of regression coefficients relating changes in the QOL-DN and other clinical endpoints to the IENFD slope, controlling for treatment assignment,

M3) Evaluation of the “proportion of the treatment effect explained by the IENFD”⁸⁴ for the QOL-DN and other clinical endpoints.

If the treatment does not affect NQOL-DN or another clinical endpoint, the M1 and M2 analyses will provide understanding of the null effect of the treatment. The evaluation of the profile of treatment effects in M1 will be performed by plotting the estimated treatment effects on each outcome with their 95% confidence intervals. Treatment effects on continuous and categorical variables will be estimated using linear or generalized linear mixed models analogous to those described in Aim 1; the treatment effect on the rate of falls will be analyzed using negative binomial regression. Concordant effects for IENFD and a particular clinical endpoint will suggest possible mediation of the treatment effect on the clinical endpoint through IENFD, whereas discordant effects will suggest IENFD did not play a major role (i.e. was not clinically relevant). Bootstrap resampling will be used to provide 95% confidence limits for ratios of treatment effects on IENFD vs. effects on the clinical endpoints.

The treatment effect estimates in the M1 analyses represent direct comparisons of randomized groups, and hence are not subject to confounding due to the randomized trial design. This is not the case for the M2 and M3 analyses, as confounding factors that jointly influence both the intermediate variables and the NQOL-DN or other clinical endpoints will lead to biased estimates⁸⁵. Failure to recognize this issue has led to confusion in prior applications of path analysis for evaluation of mediating factors⁸⁶. Thus, we will seek to identify and control for baseline and follow-up factors that may potentially influence both IENFD and NQOL-DN or other clinical endpoints in the M2 and M3 analyses.⁸⁷

The regression coefficients of the IENFD slope in the M2 analyses will provide information concerning the clinical interpretation of the IENFD slope by characterizing the difference in the 96-week change in the NQOL-DN associated with a given difference in the IENFD slope. These analyses will be carried out using a joint mixed effects model in which the NQOL-DN will be assumed to be related to the underlying random IENFD slopes. We have experience fitting similar joint models using the SAS procedure NL MIXED⁸⁸. In the M3 analyses, the proportion of treatment effect explained (PTE) by the IENFD slope on the NQOL-DN will be obtained by first estimating the total effect of the treatment on change in the NQOL-DN to 96 weeks with adjustment for potential confounders but not the IENFD slope using a mixed effects model as

described in Aim 1, and then estimating the treatment effect on the change in the NQOL-DN that remains after controlling for the IENFD slope in a joint mixed effects model which adjusts for the IENFD slope in addition to the baseline confounders. The PTE by IENFD will be estimated by subtracting the ratio of the adjusted vs. unadjusted treatment effects from 1, and a 95% confidence interval constructed using bootstrap resampling. Similar analyses will be used to estimate the regression coefficients of the IENFD slope (for the M2 analyses) and the PTEs associated with IENFD (for the M3 analyses) for other clinical endpoints. To gain further insight into the effects of the topiramate intervention on different components of quality of life, the M2 and M3 analyses will be repeated for the five individual subscales of the NQOL-DN.

